Since we are interested in better understanding feasibility of the intervention as compared to the waitlist control, and how behaviors are sustained over time, the study involves extended follow-up to six months. We will use these extended follow-up data to better understand differential attrition as well as preliminary formative implementation evaluation. Using purposive sampling, we will conduct ~ 16 indepth semi-structured interviews, 10 participants, 5 clinicians, and the health coach. Each interview will occur post-intervention and will include key stakeholders from the following groups: study participants from each arm of the pilot study, the health coach, primary care providers (including clinic leadership, geriatricians, and clinical psychologists- will be identified by the PI's professional network and via snow ball sampling), and will be audio recorded (on LRX 40 USB or UTSW digital logger) for research purposes. Each audio recording will, thereafter, be transferred to a secure folder, behind the UTSW firewall and deleted from the audio recording device. . The research staff will select participants identified as higher risk for drop-out, less engaged, or were particularly successful at achieving behavioral change. The purpose of the final interviews is to learn about the barriers and facilitators to successful intervention delivery and participant retention from the perspectives of the enrolled patients, health coach, and providers. Interview topics will borrow from components of the well-established framework, Promoting Action on Research Implementation in Health Services (PARiHS). Semi-structured interview strategy is informed by two PARiHS dimensions: context-how the microsystem (UTSW and or Parkland) impacts behavioral change uptake, for example, potential facilitators to intervention implementation; facilitation-identifying specific ways to augment the likelihood of implementation. Table 1 outlines the structure of the interview questions.

Table 1. Key Informant Interview Topics Based on PARiHS Framework of Evidence, Context, and Facilitation							
PARiHS Dimension: Evidence	PARiHS Dimension: Context	PARiHS Dimension: Facilitation					

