- Self-reported, uncorrected hearing or visual disturbance precluding ability to participate in telephone sessions or read pedometer screen
- Cognitive impairment, assessed by Memory Impairment Screen
- Lumbar surgery within the last year
- Self-reported dependence on wheelchair, bed-bound, or severe balance impairment (unable to participate in physical activity intervention)
- Illness requiring hospitalization within the last 3 months (e.g., fall, gout attacks, stroke, heart attack, heart failure, or surgery for blocked arteries)
- Suicidal ideation or prior psychotic episodes requiring hospitalization within the last year

Recruitment Strategy and Informed Consent Process

A waiver of consent for recruitment will be sought for identifying patients in the EMR, delivery of an invitation letter, and screening of potentially eligible participants aged 50 and older with an ICD-10 code for back pain and depression. We are also filing a waiver/alteration of HIPPA request to conduct the tele-delivered intervention and outcome assessments. Such a waiver is justified as minimal risk is anticipated; the waiver will not adversely affect the rights or welfare of participants.

Identified patients will be mailed an invitation letter signed by the principal investigator requesting their participation. The letters will describe the research study, describe what time involvement the project would require, and provide a local number to refuse contact. Letters will only be written in English as non-English speaking patients are ineligible for enrollment.

UTSW Strategy

The first recruitment method involves identifying when potentially eligible participants have appointments in UTSW GIM primary care clinic. The GIM provider will introduce the study and a research staff member to the patient during their clinic visit. The research staff member will then provide a detailed study overview and verbally consent the participant if interested, and ask a series of eligibility screening questions

The second recruitment method involves direct provider referral. [name] will provide a flyer to be posted in GIM primary care clinics (see attached to this IRB protocol submission) with a study synopsis and eligibility criteria. If the participant is interested in learning more, he/she may call the number

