Since we will be recruiting older adults with comorbid depression, we have a plan in place should a participant be found to have worsening mental health conditions(s). If the participant develops worsening depressive symptoms during this study, the PCP will be notified to make appropriate follow-up or evaluation with Mental Health. In the case of suicidality endorsed, as standard measures at UTSW and Parkland, we will provide the suicide [contact]-TALK)) and a local 24/7 crisis [contact]), warm transfer to mental health specialist, follow-up with mental health services, and communication with the primary care physician. If the participant endorses suicidal or homicidal ideation during an in-person interview, the participant will be escorted to the Emergency Department

for in-person psychiatric evaluation. The PI will be immediately notified of any de-escalation of mental health conditions.

A protocol will be in place should the study team identify a potential participant who reports or develops suicidal ideation. For safety purposes, the protocol is as follows: any patient identified as having suicidal ideation during this screening process will be referred to [name], their respective Emergency Department, and referred to a national [contact]-TALK) or the local [contact]). Using a pre-established protocol, [name] will contact the participant and make arrangements for immediate mental health assessment and treatment based on the participant's symptoms. All suicidal patients will be provided with the suicide crisis hotline number, regardless of other immediate clinical interventions. Furthermore, participants with severe psychiatric diagnoses (as specified among the exclusion criteria) or prior documented inpatient admissions for suicidal ideation will be excluded and not enrolled in the study.

Procedures to Maintain Confidentiality

All electronic data will be stored within password protected data management programs, on password protected computers. All research staff will be trained in the appropriate safeguarding of confidential data and in the protection of human participants. At the end of the study, after analyses are complete, all study data will be de-identified, and the identifying key will be destroyed per UTSW policies and regulations.

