All print information will be stored in locked files. The print information will be destroyed one year after the study completion date. Personally identifying data (name, address, and phone number) will be obtained from the UTSW and Parkland EMR system for the purpose of identifying potential participants and conducting calls in a secure password-protected database. Only members of the research team will have access to this information. All electronic information (survey database) will be stored on password-protected files on secure network servers. Identifiers will be destroyed after the study completion. Only IRB approved study personnel will have access to study data.

We anticipate that our procedures to minimize risk of confidentiality will be highly effective. In the unlikely event of loss of patient confidentiality, we will have a procedure in place for responding in timely and appropriate manner. The study participant who experiences loss of confidentiality will be informed by the Principal Investigator ([name]) in writing and by phone of the loss of confidentiality. UTSW and Parkland clinical leadership, the IRB, and participant will be informed in the case of such an occurrence.

Payment to Participants for Their Participation

For this study, we will provide incentives to all the participants who will be recruited (n=50). Each participant will receive a modest incentive after completion of each data collection assessment. Participants will be paid \$15 after completion of each outcomes assessment (this does not include the intervention health coaching sessions), and after completion of the in-depth interview, if selected. This will include assessments at baseline, mid-intervention at ~ five weeks, post intervention at ~10 weeks,

six-month interviews, and in-depth interview (only if selected) for a total of potentially \$60-75 if they complete all assessments of the study.

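### The safety plan for worsening mental health tells staff to notify the PI of a de-escalation, which is the reverse of what it must mean

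*Combined protocol and SAP*

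**What the plan says.** The relevant text is in Potential Risks. One paragraph there opens by stating its purpose: because the trial recruits older adults with depression, "we have a plan in place should a participant be found to have worsening mental health conditions(s". It then gives three situations and a response to each:

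- Depressive symptoms worsen: "If the participant develops worsening depressive symptoms during this study, the PCP will be notified to make appropriate follow-up or evaluation with Mental Health".
- Suicidality is endorsed: crisis-line numbers, a warm transfer to a specialist, mental health follow-up and contact with the primary care physician.
- Suicidal or homicidal ideation is voiced at an in-person interview: escort to the Emergency Department for psychiatric evaluation.

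The paragraph ends: "The PI will be immediately notified of any de-escalation of mental health conditions".

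A separate paragraph follows on suicidal ideation. It begins "A protocol will be in place should the study team identify a potential participant who reports or develops suicidal ideation", and its stated steps are tied to screening. It says that a person whose name has been removed "will contact the participant and make arrangements for immediate mental health assessment and treatment".

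**The concern.** The closing rule names a trigger that runs against the paragraph it closes. The paragraph is about decline, but the trigger word means a reduction in severity. Followed to the letter, the rule would have staff alert the PI at once when a participant improves, and would not ask for an alert when a participant gets worse.

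What is at stake is whether the PI hears promptly about deterioration. Eligibility requires a PHQ-9 above 10, and Table 2 repeats the PHQ-9 at the mid and end assessments. Outcome calls are made by a research team member and coaching is delivered by a health coach, so the people who first see a decline are likely to be study staff working by telephone or video. Potential Risks itself accepts that talking about pain or depression may cause further distress. An immediate-notification rule meant for those staff should say what it means.

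**Working it through.** The plan gives no figure on this point, so there is nothing to recompute. The check is a comparison of texts in three steps.

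**Step 1: direction of each element in the paragraph.**

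| Element | Direction | Who is told or involved |
|---|---|---|
| Opening statement of purpose | Worsening | Not stated |
| Depressive symptoms during the study | Worsening | PCP |
| Suicidality endorsed | Crisis | Crisis lines, mental health specialist and services, primary care physician |
| Suicidal or homicidal ideation in person | Crisis | Emergency Department |
| Closing rule | Lessening, as worded | PI |

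Only the last row points the other way, and it is the only row that names the PI.

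**Step 2: can another reading rescue the word?** De-escalation could mean staff calming a crisis. On that reading the PI would be told after a crisis had been calmed, and the sentence would still not call for notice when a participant declines. Urgent notice of improvement has no evident purpose in a plan for worsening. The remaining explanation is that *worsening*, *escalation* or a similar word was intended.

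**Step 3: does another sentence supply the correct trigger?** Leaving out the title line, the visible text mentions the PI in four places:

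1. Study Design, on the clinicians to be interviewed, who "will be identified by the PI's professional network and via snow ball sampling". This is not a notice to the PI.
2. Recruitment Strategy and Informed Consent Process: "Identified patients will be mailed an invitation letter signed by the principal investigator requesting their participation". This is not a notice to the PI.
3. Potential Risks: the closing rule. This is a notice to the PI, with its trigger reversed.
4. Procedures to Maintain Confidentiality: "The study participant who experiences loss of confidentiality will be informed by the Principal Investigator". This is a notice from the PI, not to the PI.

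So 1 of 4 mentions is a notice to the PI. Of the other 4 − 1 = 3, none gives the PI notice of a participant's mental state. Removed names are not counted, because their roles cannot be known from the text. The tally shows only that no visible sentence corrects the rule. It does not measure how serious the slip is.

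**The case against.** The strongest reply is that nobody would be misled. The paragraph announces its subject as worsening, every event in it is a deterioration, and a coordinator reading it would understand the last sentence as intended. On this view the slip is a matter for a proofreader. Participants are also protected without it, since each clinical step stands on its own. Both points are right, and they are why the matter is minor.

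A second reply concerns the removed name in the paragraph on suicidal ideation. That person may be the PI. Although the steps there refer to screening, the opening also covers someone who develops ideation. The PI may therefore be brought in by another route, and text missing through removal of names cannot be held against the plan. This limits the claim to there being no other visible, explicit notice to the PI. It does not support saying that no route exists, and nothing is claimed here about screening. It also does not settle the matter in the plan's favour: even if that person is the PI, the paragraph deals with suicidal ideation and would not cover depression that worsens short of it.

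Neither reply makes the word correct. The sentence is an instruction that staff are expected to act on, and they should not have to infer that it means its opposite.

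**Conclusion.** The concern holds. The trigger for notifying the PI is reversed as written, and the error can be verified from the paragraph alone, so confidence is high. Its extent is one word, and the possible effect is confined to how promptly the PI learns of a decline. The documents give no rate of such events, so no number of missed notices is claimed, and no harm is asserted. Sample size, error rates, endpoints and analyses are untouched. Severity is minor.

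The conclusion rests on two things: the ordinary meaning of *de-escalation*, and the visible text, with the roles of the people whose names were removed left open.

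**What to change.** In the closing sentence of the paragraph, replace *de-escalation* with *worsening* and leave the rest as it stands. The sponsor may also add that this includes any suicidal or homicidal ideation. That addition is optional, since *worsening* read with the preceding sentences arguably covers it already.

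The cost is one word at the next amendment. Procedures, data collection and analysis do not change.

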 Perceptions about the strength and motivation for personalized goal-setting Perceptions about how well goal-setting is accepted by adults Perceptions of how goal-setting affects current practices or can be integrated into routine work flows Perceptions of how patient activation can be applied to improve outcomes Perceptions of how motivations to change and identifying meaningful goals can be aligned 	 Availability of resources to carry out personalized goal-setting How training and fidelity assessment for personalized goal-setting fit with work demands Past experiences with collaborating with other health care providers on self-management or goal-setting Existing channels of communication for input and feedback among health care providers regarding goal-setting and self-management 	 How to align roles in the project with existing responsibilities Perceptions about what successful implementation will require from staff, patients, and clinicians Perceptions of skills, attitudes, and beliefs about internal facilitators and study team Plans for establishing formal communication routines between study team, health care providers and other personnel 					

Criteria for Inclusion of Participants

Participant Selection

An initial data pull using patients' electronic medical records (EMR) will identify a pre-screen list of potentially eligible patients. Potential participants will include only those with an International Classification of Diseases-10 (ICD-10) code for back pain and depression. Further eligibility criteria are as follows:

Inclusion Criteria

- Aged 50 and older
- English- speaking
- Working telephone
- Capable of participating in home-based activity
- Chronic low back pain with intensity of 4 or higher on 10 point scale
- At least one doctor visit for cLBP in the two years
- UTSW General Internal Medicine (GIM) or Parkland internal medicine/primary care clinic or community outpatient clinic patient with scheduled clinic appointment within 2 years of enrollment date
- Self-reported low back pain (+/-radiation) in the past 3 months that interferes with daily activities on most days

 Depression, PHQ-9>10 stable (per chart review, no psychotic or suicidal ideation; confirmed over telephone or video-assist)

Exclusion Criteria:

- Aged 49 or less
- No telephone
- Not English speaking
- Unwilling to be randomized to either study arm

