Study data will be stored within password protected data management programs, on password protected computers. Only IRB approved study personnel will have access to study data. All research staff will be trained in the appropriate safeguarding of confidential data and in the protection of human participants. At the end of the study, after analyses are complete, all study data will be de-identified, and the identifying key will be destroyed per UTSW and Parkland policies and regulations. The health coach will have restricted access to the study database; he/she will also have access to EMR as needed.

Outcome Assessments and Data Collection

Using age >50, ICD-10 codes for chronic back pain and depression as criteria, an initial data pull from patients' EMR will yield a list of potentially eligible prospective study participants. The research team will pre-screen this list of potentially eligible patients for recruitment. As outlined in section **Recruitment Strategy and Informed Consent Process**, participant recruitment may occur in-person or by tele-based method and will include an introduction to the study and **verbal consent**. Upon completion of consent, a research staff member will further screen for eligibility and arrange a separate telephone call for a baseline assessment. As seen in the **Figure 2** below, a research team member, not the health coach, will complete all outcome assessments via telephone using structured data collection tools at baseline, midpoint (~ 5 weeks), end-point (~ 10 weeks), and 6 months post-intervention. A subset of the participants from the trial will be invited for an in-depth, semi-structured interview, as discussed above (Aim 2), to better understand implementation and sustainability of behavior uptake.

All study-related data from the assessments will be entered into a UTSW REDCap database at: https://ais.swmed.edu/redcap/. Only de-identified data will be entered in REDCap. The health coach or a research staff member will obtain daily versus weekly step counts from study participants as appropriate depending on the session content and activity tracker assignment.

Outcome Measures

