 their associated diagnosis/procedure codes (which our research team will use to determine if pain,
 degenerative joint disease, depression-related).

Table 2. Demographic and Clinic	al Data Poin		come Asses	sment Instr	ument	5
DATA	SOURCE	PRE- SCREEN	SCREEN	BASELINE	MID	END
Sex	EMR	Х		Х		
Age 50+	EMR	Х		Х		
ICD-10 back pain	EMR	Х				
ICD-10 depression	EMR	Х				
History of suicidal ideation	EMR	X				
Psychotic or suicidal hospitalization w/ past year	EMR	Х				
Telephone	EMR	Х				
	Phone					
Inclusion/Exclusion Criteria						
50 or older (confirm)	Phone		Χ			
(Clbp confirm) Low back pain (+/-radiation) on most days for the past 3 months?	Phone		Х			
(Clbp confirm) Does your back pain limit your ability to do activities around the home or activities that you enjoy?"	Phone		Х			
Rate pain level in past week (Scale 0-10)	Phone		Х	Х	Х	Х
Self-report hearing/visual challenges	Phone		Х			
Lumbar surgery within past year	Phone		Χ			
Recent illness/diagnosis of concern	Phone		Х			
Bed bound	Phone		Х			
Use of wheelchair around the house	Phone		Х			
Safety & Physical Activity	Phone		Х			
Cognitive Screener	Phone		Х			
Patient Health Questionnaire (PHQ-9)	Phone		Х	Х	Х	X
Self-Report Demographics and Other	Clinical Vari	ables				
Race/Ethnicity	EMR Phone			Х		
Education	EMR Phone			Х		
Marital Status	EMR Phone			Х		
Living situation	EMR Phone			Х		
Address	EMR Phone			Х		

Charleston Age Comorbidity	EMR	Х		
Calculator				
Body mass index	EMR	Х		
Medication list	EMR	Х		
	Phone			
Pain injections at ER/outpatient in	EMR	Х	Х	Х
the last month				
Med/mental/PT appointments	EMR	Х	Х	X
(related to Clbp/depression) or	Phone			
ED/urgent care visits within the last				
6 months				
Financial situation	Phone	Х		
Most frequented primary care clinic	Phone	Х		
location				
Short Michigan Alcoholism	Phone	Х		Χ
Screening Test (SMAST)				
Drug Use Questionnaire (DAST)	Phone	Х		
Expectation of Intervention	Phone	X		
Pain Screen Tool (PEG)	Phone	X	Х	Χ
Self-Efficacy Arthritis	Phone	X	Х	Х
Roland Disability Quest: Rating	Phone	Х	Х	X
Scale for Low Back Pain				
Pain Catastrophizing Scale (PCS-EN)	Phone	X	Х	Х
Fear Avoidance Beliefs	Phone	Х	Х	X
Questionnaire (FABQ)				
Physical Activity Contemplation	Phone	Х	Х	Х
Ladder				
Exercise Questionnaire	Phone	Х	Х	Χ
General Health Questions	Phone	X	Х	Х
Pain Stage of Change	Phone	Х	X	Χ
PROMIS 1.2 Global Mental Health	Phone	Х	X	Χ
PROMIS 1.2 Global Physical Health	Phone	Х	Х	X
PROMIS SF 1.1 Pain Behavior	Phone	Х	X	Χ

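### The safety section bars any past inpatient admission for suicidal ideation, but the Table 2 hospitalization row looks back one year and the exclusion bullet does not state the any-time rule

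*Combined protocol and SAP*

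**What the plan says.** Four places in the combined protocol and SAP bear on a patient's suicide history at entry.

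- **Potential Risks**, at the end of the paragraph on suicidal ideation at screening, says that people with "prior documented inpatient admissions for suicidal ideation will be excluded and not enrolled in the study". No look-back period is given.
- **Exclusion Criteria** has one related bullet: "Suicidal ideation or prior psychotic episodes requiring hospitalization within the last year".
- **Table 2** has two relevant rows, both taken from the EMR at pre-screen: "History of suicidal ideation", with no window, and "Psychotic or suicidal hospitalization w/ past year".
- **Inclusion Criteria**, in the depression line, requires by chart review "no psychotic or suicidal ideation; confirmed over telephone or video-assist". No window is given here either.

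Outcome Assessments and Data Collection describes how the EMR list is used: "The research team will pre-screen this list of potentially eligible patients for recruitment". Further eligibility screening follows consent.

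Separately, the Potential Risks paragraph on events during the study opens by saying "we have a plan in place should a participant be found to have worsening mental health conditions(s" and ends with "The PI will be immediately notified of any de-escalation of mental health conditions".

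**The concern.** The trial selects older adults for depression, so the rule on suicide history is a working safety rule. If the safety section applies it without a time limit while the screening table applies it for one year, two staff members following different sections can reach opposite decisions on the same patient. A person whom the safety section says will not be enrolled could then pass screening.

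The notification sentence is a smaller matter. Its trigger word means the opposite of what the paragraph is about.

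**Working it through.** No arithmetic applies; the check compares the texts. Take a patient admitted for suicidal ideation 18 months ago, with no ideation since.

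| Place | Look-back | Result for this patient |
|---|---|---|
| Potential Risks | None stated | Excluded |
| Table 2, hospitalization row | One year | Not flagged |
| Table 2, ideation-history row | None stated | Flagged if charted; consequence not stated |
| Exclusion Criteria bullet | Depends on the reading | Not expressly excluded |
| Inclusion Criteria, chart review | None stated | May be noticed; the criterion concerns ideation, not admission |

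**The exclusion bullet.** Its wording can be parsed in more than one way.

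1. Both the hospitalization and the one-year window qualify suicidal ideation and psychotic episodes alike. An admission 18 months ago falls outside the window.
2. The window qualifies both conditions, but the hospitalization only the psychotic episodes. Ideation 18 months ago again falls outside.
3. Suicidal ideation stands alone, with no window. The patient is excluded only if past ideation counts, and then because of the ideation, not the admission.

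None of these says that an admission at any time excludes. The Table 2 hospitalization row, which puts psychotic and suicidal stays under a single one-year limit, lends some support to the first parsing. If that is the meaning, the list and the table say one year while Potential Risks says ever.

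**The cross-reference.** The Potential Risks sentence does point to the exclusion criteria, but the parenthesis that does so follows the severe psychiatric diagnoses. The admission rule comes after it, so the parenthesis does not clearly import the one-year window.

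**The backstops.** The history row and the chart review could each surface the older admission. Neither states the admission rule, and no section says that a positive history alone excludes. No phone-screen row in Table 2 names a past psychiatric admission.

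**The notification word.** In that paragraph, the step for worsening depressive symptoms names the primary care physician. The step for suicidality lists crisis lines, mental health services and the primary care physician. The last sentence is the only one there that names the PI, and its trigger is de-escalation.

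**The case against.** The strongest reply is that the screening process as a whole would probably catch this patient. A documented admission for suicidal ideation is itself a documented history of suicidal ideation, so the open-ended Table 2 row covers it. Chart review, confirmation by telephone or video, and a further screen after consent all follow. A reader might infer that Table 2 looks back only one year, or that the exclusion list says nothing on the subject. The documents support neither: Table 2 has the unlimited history row, and the list has a related entry with a one-year window. This is a conflict between windows, not silence. It would equally be wrong to count the possible parsings of the bullet and present the count as a size.

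It can also be said that Potential Risks is a narrative restating the eligibility list in shorthand. That is possible, but the sentence is worded as a rule on enrollment and is broader than the list it would be restating.

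On notification, a reader might infer that the PI will hear of improvement and not of deterioration. That is too literal. The paragraph concerns worsening, immediate notification makes sense only for worsening, and the other protective steps are triggered correctly. The intent is plain.

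What survives is narrower. The history row has no stated consequence, so catching the older admission depends on staff linking that row to a rule found only in the safety section.

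**Conclusion.** Wrong as written, and minor. The sections that govern entry do not give one answer for a patient whose admission for suicidal ideation is more than a year old. Such a patient could be passed at screening against the safety section. That is a possibility, not a demonstrated failure, because the history row and the chart review may intervene.

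The conclusion rests on taking the Potential Risks sentence as an operative rule and on reading its cross-reference as limited to psychiatric diagnoses. The number of patients affected cannot be derived from the documents. No estimate, sample size or analysis changes.

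The notification word is a wording slip with clear intent. It should be corrected because an instruction for immediate action should not depend on inference.

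**What to change.** Keep the stricter rule that the safety section already states, and bring the other sections into line with it.

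1. **Exclusion Criteria.** Split the bullet into three lines: (a) suicidal ideation, unchanged as an exclusion; (b) any documented past inpatient admission for suicidal ideation, whenever it occurred; (c) a psychotic episode that led to hospitalization in the past year.
2. **Table 2.** Remove the one-year limit for suicidal hospitalization and keep it for psychotic hospitalization.
3. **Table 2, ideation-history row.** State that a positive entry triggers a check of the record for any past admission.
4. **Potential Risks.** Have the PI notified of worsening, in place of de-escalation.

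The cost is wording in three places and the matching item on the screening form, plus a record check when the history row is positive. No visit or assessment is added. The downside is that a few more patients may be screened out.
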